## 5.4 Study Subjects

A clear accounting of the disposition of all participants with number and percentages of participants for whom No Objection Letter is obtained (Yes/No), Participants having NOL waiver (including deceased participants)-Yes/No, participants not meeting inclusion and exclusion criteria with primary reason for screen failure, participants meeting inclusion/exclusion criteria and participants receiving at least one dose of osilodrostat, and participants who discontinued prematurely (including death) by reason will be provided.

A listing of the participant disposition with the above details will be provided as per the eCRF.

#### 5.5 Protocol Deviations

Major protocol deviations are defined as those deviations from the protocol that are likely to have an impact on the participant's rights, safety, well-being, and/or on the validity of the data for analysis.

The number of participants with protocol deviations will be summarized by category (Major or Minor) and deviation classification. Protocol deviations will be listed with date and study day of occurrence, deviation category, deviation description and analysis populations from which participant is excluded.

#### 5.6 Demographic and Other Baseline Characteristics

A summary of demographic and baseline characteristics will be provided including Age (years), Gender, Height (kg), BMI (kg / m^2).

A summary of clinical (disease) characteristics will include putative causation (i.e., adrenal adenoma, adrenocortical carcinoma, ectopic adrenocorticotropic hormone secretion, adrenal hyperplasia) and date of Cushing's syndrome diagnosis.

Descriptive summary statistics (n, mean (SD), median, minimum, maximum) or number and percentages will be provided for participants as applicable for the above-mentioned demographic components.

A participant level listing will be provided with all details of demographic components as per the eCRF.

# 5.7 Medical and procedural/surgical history

Medical and surgical history will be presented in a descriptive manner including number and percentages of past or current significant medical and surgical conditions.

A participant level listing of significant medical and surgical history will be provided with details of past or current significant medical or surgical history as per the eCRF.

Project Document Version No.: 4.0; Document Effective Date: 30 October 2023

CONFIDENTIAL

TP-GDO-WW-096-09 Effective Date: 22 Dec 21

Related to: SOP-GDO-WW-019

#### 5.8 Prior and Concomitant Medications

The prior and concomitant systemic therapy, radiotherapy and surgical therapy will be summarized in similar manner as described.

Medication start and stop dates will be compared to the date of first dose of osilodrostat to allow medications to be classified as either Prior only, both Prior and Concomitant, or Concomitant only. Medications starting after the completion/withdrawal date will be listed but will not be classified or summarized.

Medications that start and stop prior to the date of first dose of osilodrostat will be classified as Prior only. If a medication starts before the date of first dose of osilodrostat and stops on or after the date of first dose of osilodrostat, then the medication will be classified as both Prior and Concomitant. Medications will be classified as Concomitant only if they have a start date on or after the date of first dose of osilodrostat.

If medication start and/or stop dates are missing or partial, the dates will be compared as far as possible with the date of first dose of osilodrostat (see section 5.11.2). Medications will be assumed to be Concomitant only, unless there is clear evidence (through comparison of partial dates) to suggest that the medication started prior to the first dose of osilodrostat. If there is clear evidence, such as an ongoing medical history with the same indication, to suggest that the medication started prior to first dose of osilodrostat and with no stop date, the medication will be assumed to be both Prior and Concomitant. If there is clear evidence to suggest that the medication stopped prior to first dose of osilodrostat, the medication will be assumed to be Prior only.

# 5.9 Safety Analysis

#### 5.9.1 Adverse Events

All AEs, whether they are serious/non-serious, related/unrelated, and all "special situations" reported in participants' charts within the data collection period should be collected. All AEs will be assessed according to incidence, grade, causality, outcome, action taken and seriousness.

TEAE and AESI were defined in section 5.3.3.5

An overview of adverse events will summarize the percentage of participants experiencing deaths, SAEs, AE reported as reason for discontinuation, TEAEs, and AEs possibly related to study drug.

The frequency and percentage of participants with following will be summarized using MedDRA preferred Term nested within SOC.

- TEAE
- TEAE by maximum severity
- TEAEs related to osilodrostat
- TEAE leading to osilodrostat dose interruption/adjustment
- TEAEs leading to study discontinuation
- SAEs including death
- SAEs by maximum severity
- SAEs related to osilodrostat
- Deaths
- AE of Special Interests (AESIs)

Project Document Version No.: 4.0; Document Effective Date: 30 October 2023

CONFIDENTIAL

RECORDATI AG, Rare Diseases Branch LCI699-RECAG-NI-0596

Statistical Analysis Plan

Adverse event summaries will be ordered in terms of decreasing frequency for SOC, and PT within SOC. For incidence counts, each participant will be counted only once within each Preferred Term and within each SOC. Percentages will be based on the number of participants in safety population. For events that are gender-specific, the denominator and computation of the percentage will include only participants from the given gender.

By-participant listings of all adverse events (including non-treatment-emergent events) recorded on the CRF, all TEATs, TEAEs leading to study discontinuation, SAEs including death, and deaths during the treatment period will be presented by participant, visit, preferred term, severity, and relationship to the study drug.

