8.7.9 Analysis of Secondary Endpoints

Changes from baseline for biochemical variables and clinical outcomes to Week 4, 8, 12, 18, 24, 36, and to every 12 weeks until the earlier of loss to follow-up, death, or the end of the retrospective follow-up period or treatment discontinuation will be summarised descriptively and provided as listing.

Final v2.0 50 of 63 18 April 2023

Baseline is defined as the available value at the time of osilodrostat initiation or the closest value within 2 weeks prior to osilodrostat initiation. Change from baseline will be calculated as the visit value of interest minus the baseline value.

For secondary variables, refer to Table 1.

Change from initial dose

The extent of exposure will be provided by summarising the description of initiating dose (and date) of osilodrostat, and up- and/or down-titration regimen (dose increases/decreases, date).

Proportion of patients who experienced TEAEs and AESIs

An overall summary table of all treatment-emergent adverse events (TEAEs) will be presented with the number and proportion of participants and the number of events. Summary incidence tables of all TEAEs (through Week 12 and follow-up at every 12 weeks until the earlier of loss to follow-up, death, or the end of the retrospective follow-up period, or treatment discontinuation), SAEs and TEAEs by severity grade and relationship to study drug will be provided, classified by primary System Organ Class (SOC) and Preferred term (PT).

All AEs will be coded according to the latest version of the Medical Dictionary for Regulatory Activities and will be classified by MedDRA PT and SOC.

All safety data will be included in the participant data listings, such as listings of all TEAEs, SAEs, TEAEs leading to study drug withdrawal and listings of deaths.

Summary incidence tables of select AEs specific to CS (AEs of fatigue, nausea, vomiting, headache, backache, oedema, clinical features including acne, hirsutism, laboratory abnormalities including hypokalaemia or hyperkalaemia, and hypertension) by severity grade and relationship to study drug will be provided, classified by primary SOC and PT.

Adverse Events of Special Interest (AESI) will be defined as following AEs:

Final v2.0 51 of 63 18 April 2023

Adrenal hormone precursor accumulation-related AEs

- - o Hypocortisolism-related AEs
 - o Pituitary tumour enlargement-related AEs
 - o Arrhythmogenic potential and QT prolongation AEs

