The frequency and percentage of patients experiencing treatment emergent AESI will be summarised by severity grade and relationship to study drug and will be provided, classified by primary SOC and PT.

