### **On-Treatment Population**

The On-Treatment population consists of all participants while they are taking osilodrostat at a defined timepoint or period.

- In circumstances where end of treatment date is missing and patient did not change to 0mg prior
  to end of study, the end of study date will be considered as end of treatment date if end of study
  reasons were due to adverse event, death, osilodrostat permanently discontinued, administrative
  reasons (no data reported), end of retrospective follow-up period.
- For cases where last recorded dose was changed to 0mg prior to the end of study, then the date
  when dose changed to 0mg will be considered as the last date of exposure (i.e., end of treatment
  date).

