#### 5.3.3.11 Proportion of participants who experienced TEAE and AESI

A treatment-emergent adverse event (TEAE) is defined as an AE that begins or that worsens in severity after at least one dose of osilodrostat has been administered. The start date of adverse events will be compared with date of first dose of osilodrostat and the date of the earlier of loss to follow-up, death, the end of the retrospective follow-up period or treatment discontinuation occurs, whichever is earlier.

TEAE will be coded according to the latest Medical Dictionary for Regulatory Activities (MedDRA) terms and summarized by MedDRA System Organ Class (SOC) and Preferred Term.

Adverse Events of Special Interest (AESI) will be defined as following AEs:

- Adrenal hormone precursor accumulation-related AEs
- Hypocortisolism-related AEs
- Pituitary tumour enlargement-related AEs
- Arrhythmogenic potential and QT prolongation AEs

All AEs will be assessed according to incidence, grade, causality, outcome, action taken and seriousness. The details are provided in the safety analysis section 5.10.1 below.

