#### 5.13 CHANGES FROM PROTOCOL

Currently the SAP elaborates analyses as planned in the protocol and some related analysis in addition to protocol specified analysis. This section is kept for documenting any changes made to the planned analyses in the study protocol due to various circumstances for e.g., a protocol amendment. Any such changes (if occurs) will be documented, and this section of SAP will be updated with all necessary details related to the change.

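### SAP 5.9.1 and 5.10 do not carry forward three safety outputs that protocol 8.7.9 specifies, and SAP 5.13 declares no change

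*SAP*

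**What the plan says.** Protocol 8.7.9 sets three outputs that matter here.

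- **AESIs:** "The frequency and percentage of patients experiencing treatment emergent AESI will be summarised by severity grade and relationship to study drug", classified by system organ class (SOC) and preferred term (PT).
- **Drug withdrawal:** participant listings, "such as listings of all TEAEs, SAEs, TEAEs leading to study drug withdrawal and listings of deaths".
- **CS-specific events:** "Summary incidence tables of select AEs specific to CS (AEs of fatigue, nausea, vomiting, headache, backache, oedema", continuing with clinical features, potassium abnormalities and hypertension, again by severity and relationship. Protocol Table 1 also names CS-specific TEAEs as a secondary variable.

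SAP 5.9.1 lists the tables to be produced by PT within SOC. The AESI entry is "AE of Special Interests (AESIs", with no further qualifier. The discontinuation entry is "TEAEs leading to study discontinuation", and the same event is used for the listing. There is no CS-specific entry. For subgroups, SAP 5.10 iii also asks for AESIs by SOC and PT only.

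Protocol 8.7 requires changes to its analysis methods, where they do not need an amendment, to be described and justified in the final SAP. SAP 5.13 states: "Currently the SAP elaborates analyses as planned in the protocol and some related analysis in addition to protocol specified analysis". It records no removal.

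**The concern.** AESI incidence is part of a named secondary endpoint in both documents (protocol Table 1; SAP 3.6.2 e), and the study is meant to support a supplemental application to the FDA. Tables are programmed from the SAP. Other rows in 5.9.1 state whether they are treatment-emergent, by maximum severity or drug-related, so an AESI row with none of these would naturally be programmed with none of them.

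Three things are at stake: whether the AESI proportion describes events under osilodrostat; whether stopping the drug because of an adverse event has a clearly defined output; and whether a prespecified safety grouping disappears without a recorded reason.

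**Working it through.** No formula applies and the plan gives no figure to reproduce. The check is a comparison of the two texts.

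1. **Which AESI wording changed.** SAP 5.3.3.11 introduces four classes with "Adverse Events of Special Interest (AESI) will be defined as following AEs". Protocol 8.7.9 uses the same lead-in and the same four classes, so the definition is unchanged. The treatment-emergent restriction sat in the protocol's table specification, and that specification was not carried over.

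2. **Whether the restriction can alter the count.** It can only if events from before the first dose are in the database. Protocol Table 2 and SAP Table 1 both mark adverse events at baseline. SAP 5.9.1 plans a listing that includes non-treatment-emergent events. SAP 5.11.2 has imputation rules for partial event dates falling in a month or year before the first dose. So it can.

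3. **How far it can alter the count.** Protocol 8.1 has abstraction start at osilodrostat initiation. Footnote a to Table 2 lets the baseline column reach back at most 2 weeks. Footnote h sends earlier CS-related conditions to medical history. These limits point to few such events. With about 100 patients (protocol 8.5), each patient whose only AESI-class event preceded the first dose would add about 1/100, or one percentage point. The documents do not say how many such patients there are.

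4. **Grade and relationship.** SAP 5.9.1 specifies maximum-severity and drug-related tables for TEAEs and for SAEs, but not for AESIs. Grade and causality are still assessed for every adverse event, and the listings show severity and relationship. The loss is confined to the grouped AESI tables.

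5. **Drug withdrawal against study discontinuation.** The protocol asks for a listing. The SAP gives a table and a listing, but of a different event. Follow-up ends at treatment discontinuation (protocol 8.1; SAP section 3), so the two sets largely overlap. They are not identical. The SAP's On-Treatment definition and its 5.9.5 both provide for a dose of 0 mg before end of study. The end-of-study reasons in the date rule, "adverse event, death, osilodrostat permanently discontinued, administrative reasons (no data reported), end of retrospective follow-up period", keep adverse event and permanent discontinuation apart. Of the other SAP outputs, one covers dose interruption or adjustment, and an overview line counts adverse events given as the reason for discontinuation without saying whether of drug or study. No output is clearly defined as TEAEs leading to a permanent stop of osilodrostat.

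6. **CS-specific table.** It appears in none of SAP 3.6.2, 5.3.3.11, 5.9 or 5.10. Its component events would appear by PT in the general TEAE tables.

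7. **Cross-references.** SAP 5.9.1 sends the reader to 5.3.3.5 for the TEAE and AESI definitions. That section covers change from initial dose; the definitions are in 5.3.3.11. In turn, 5.3.3.11 points to a section 5.10.1, but the adverse event section is 5.9.1.

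**The case against.** The best defence is that little information is lost. SAP 5.3.3.11 sets out the comparison of event dates with the first dose just before its AESI list, so a programmer might apply the treatment-emergent rule to AESIs anyway. The endpoint wording in protocol Table 1 does not carry the restriction either. Potassium is covered by the laboratory grading and shift tables in 5.9.3, and blood pressure and physical signs by 5.9.4. Disposition is reported by reason, and the SAP adds outputs that protocol 8.7.9 did not name, such as SAEs by maximum severity. All of this stands, and it limits the point. It does not supply the three outputs or the entry that 5.13 should contain.

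A reader might infer more than the documents support:

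- **That AESI incidence is overstated.** Including pre-dose events is the literal reading of the row, but not the only one, and no count is given. Examples such as pre-dose hypokalaemia, or hypocortisolism under an earlier drug in the switch group, cannot be confirmed: neither document lists the preferred terms in the four classes, and protocol 8.7.9 names hypokalaemia among the CS-specific events.
- **That AESIs are no longer graded.** They are graded and listed; only the AESI table by grade is missing.
- **That withdrawals for adverse events are understated.** This would require the TEAE row to be derived from the end-of-study reason. No section says so. The reasons quoted come from a rule for imputing end-of-treatment dates, and the SAP says adverse events are assessed by action taken.

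**Conclusion.** The point holds as an undeclared mismatch between protocol and SAP in three named safety outputs. The AESI output has lost its treatment-emergent restriction and its breakdown by severity and relationship; the drug-withdrawal output now describes an overlapping but different event; the CS-specific table is missing.

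No bias in a reported rate is shown. The effect of pre-dose events on the AESI proportion is unknown in size and probably small, on the assumption that abstraction keeps to the initiation date and the 2-week baseline window. The difference between drug and study discontinuation depends on how many patients stopped the drug before their recorded end of study, which the documents do not give. The point concerns these three outputs, not safety reporting as a whole. It should be corrected because it touches a named secondary endpoint and the correction is cheap.

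**What to change.** - **AESIs:** in SAP 5.9.1 and 5.10 iii, replace the AESI row by treatment-emergent AESIs, overall, by maximum severity grade and by relationship.
- **Drug withdrawal:** in 5.9.1, add a table and listing of TEAEs leading to permanent osilodrostat discontinuation, derived from the action-taken field of the adverse event record. State in the overview line whether discontinuation means drug or study.
- **CS-specific events:** restore the table by severity and relationship, or justify its removal in 5.13.
- **Change log:** record and justify in 5.13 any departure from protocol 8.7.9 that is intended.
- **Cross-references:** in 5.9.1, change 5.3.3.5 to 5.3.3.11; in 5.3.3.11, change 5.10.1 to 5.9.1.

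The cost is SAP wording and a few extra tables. Grade, causality and action taken are already assessed under 5.9.1, so no new data are needed.

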#### 5.9.2 Deaths

A summary of all deaths and cause of death will be tabulated. The primary cause of death collected on the AE CRF page will be reported. If the primary cause of death is AE, the number of participants who have related AE and unrelated AE will be further reported.

A listing of all deaths will be provided.

#### **5.9.3 Clinical Laboratory Evaluation**

For analysing laboratory results, data from all sources (local laboratories) will be combined. The summaries will include all laboratory assessment. All laboratory assessments will be listed. Results will be reported for each visit at which collected through the last study visit.

Eligible laboratory data will be classified into grades according to NCI CTCAE v5.0. The calculation of CTCAE grades will be based on the observed laboratory values only, clinical assessments will not be considered.

CTCAE Grade 0 will be assigned for all non-missing values not graded as 1 or higher. Grade 5 will not be used. For laboratory tests that are graded for both low and high values, summaries will be done separately and labelled by direction, The following summaries will be produced for the laboratory data (by laboratory parameter):

For laboratory tests where grades are defined by CTCAE

- Number and percentage of participants with worst post-baseline CTCAE grade (regardless of the baseline status). Each participant will be counted only for the worst grade observed post-baseline
- Number and percentage of participants meeting categorical liver function test criteria, including Hy's Law criteria for liver injury (ALT or AST > 3 x ULN and TBIL ≥ 2 x ULN and ALP < 2 x ULN). Each participant will be counted only for the worst grade observed post-baseline
- Shift tables from baseline to the worst post-baseline value and from baseline to the last postbaseline values using CTCAE grades will be produced for haematology, biochemistry, and urine laboratory parameters with CTCAE grades.

For laboratory tests where grades are not defined by CTCAE

Shift tables from baseline to the worst post-baseline value and from baseline to the last post-baseline values will be produced using the low/normal/high classifications based on laboratory reference ranges.

Scheduled visit, and unscheduled visits will be included in above analysis.

Project Document Version No.: 4.0; Document Effective Date: 30 October 2023

CONFIDENTIAL

TP-GDO-WW-096-09 Effective Date: 22 Dec 21

Related to: SOP-GDO-WW-019

Selected laboratory data will also be displayed by presenting summary statistics of change from baseline value.

The following listings will be produced for the laboratory data:

- Listing of all laboratory data with values flagged to show the corresponding CTCAE grades the classifications relative to the laboratory reference ranges
- Listing of notable laboratory abnormalities (i.e. CTCAE grade 3 or 4 laboratory toxicities).

# 5.9.4 Vital Signs, Physical Findings and Other Observations Related to Safety

#### Vital Signs

Vital signs of participants will be summarized include blood pressure (systolic and diastolic), weight, and BMI. Vital signs will be summarized for baseline, all post-baseline visits, and change from baseline to post-baseline visits. Descriptive statistics i.e., number (n), mean (SD), minimum (Min), median, maximum (Max), first and third quartiles and 95% CIs for means/medians, will be provided for systolic, diastolic blood pressure (mmHg) weight (kg), and BMI (kg/m²).

The percentages of participants with treatment-emergent high or low vital signs at any time during the treatment period will be summarized. A treatment-emergent high results is defined as a change from a value less than the high limit at all baseline visits to a value greater than or equal to the high limit at any time during the treatment period. A treatment emergent low result is defined as a change from a value greater than the low limit at all baseline visits to a value less than or equal to the low limit at any time during the treatment period. For each vital sign, only participants who were normal (i.e., less than the high limit for treatment-emergent high, or greater than the low limit for treatment-emergent low) at all baseline visits and who have at least one non-missing post-baseline result will be included in the denominator when computing the percentages of participants with treatment -emergent high or low results. Table 2 will be used to define the low and high limits.

A participant level listing will be provided for vital signs with all required details as per the eCRF.

Table 2 Selected Categorical Limits for Blood Pressure, and Weight

Parameter	Low	High
Systolic BP (mm Hg) (supine or sitting – forearm at heart level)	≤90 and decrease from baseline ≥20	≥140 and increase from baseline ≥20
Diastolic BP (mm Hg) (supine or sitting – forearm at heart level)	≤50 and decrease from baseline ≥10	≥90 and increase from baseline ≥10
Weight (kg) (consistent clothing and timing in relationship to meals and voiding)	(Loss) decrease from baseline ≥ 7%	(Gain) increase from baseline ≥ 7%

